6.2.8 Immunogenicity

The serum samples to measure the presence of ADA will be collected as specified in the Schedule of Assessments (Section 3.4). Blood samples (4 mL) to provide approximately 1.5 mL of plasma for anti BOS161721 antibody analysis will be collected into appropriately labeled tubes containing K₂EDTA. The presence or absence of ADA will be determined in the serum samples using validated bioanalytical methods. Blood samples for ADA analysis will be collected up to Day 90 from all patients. Subsequent ADA samples will be collected from all patients but only assayed if the patient had a positive ADA on Day 90.

After the first dose, if a patient tests positive in the validated confirmatory ADA assay, the sample from this patient will be further analyzed in the neutralizing antibody (nAb) assay.

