	
Safety
 
 • To assess safety and tolerability of repeat doses of BOS161721 (20, 60, and 120 mg) administered SC in adult patients with moderately to severely active SLE on limited background standard of care treatment 	
Safety Endpoints
 
 • Incidence and severity of adverse events (AEs) and serious adverse events (SAEs), related AEs, AEs leading to study drug discontinuation, AEs by severity and relatedness • Injection site reactions • C-SSRS • 12-lead ECGs parameter results at each visit and change from baseline • Vital signs (blood

Section	Description of Changes	Rationale
		pressure [BP], heart rate, and temperature) parameter results at each visit and change from baseline 
 • Clinical laboratory results and change from baseline • Physical examinations changes from baseline • ADAs • Study drug exposure/compliance • Concomitant medication usage
	Exploratory	

 • CCI [REDACTED] 	
 • CCI [REDACTED] 	
 • CCI [REDACTED]

 • CCI [REDACTED] 	
 • CCI [REDACTED] 	
 • CCI [REDACTED]

 • CCI [REDACTED] 	
 • CCI [REDACTED] 	
 • CCI [REDACTED]

Section	Description of Changes	Rationale
PROTOCOL SUMMARY , Study Design	Replace: The trial will consist of a staggered MAD Phase 1b and POC Phase 2 studies. Both studies will be double blinded with each patient having the same number of doses (7), and visits; the duration will be 180 days, followed by a 90-day follow-up safety observation period. With: The trial will consist of 2 double-blinded studies : MAD Phase 1b and POC Phase 2. Patients may receive a total of 7 SC monthly doses of study drug on Days 0, 30, 60, 90, 120, 150, and 180, followed by safety follow-up visits at Days 210, 240, and 270.	Clarification that patients will not have the same number of visits in both studies.

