2.1 Phase 1b Multiple Ascending Dose

OBJECTIVES	ENDPOINTS
Primary	

 To assess safety, tolerability, and immunogenicity of repeat doses of BOS161721 (20, 60, and 120 mg) administered SC in adult patients with moderately to severely active SLE on limited background standard of care treatment, in order to estimate the optimal dose. 	Safety Endpoints 
 Incidence and severity of adverse events (AEs) and serious adverse events (SAEs), related AEs, AEs leading to study drug discontinuation, AEs by severity and relatedness Injection site reactions Columbia Suicide severity Rating Scale (C-SSRS) 12-lead electrocardiograms (ECGs) parameter results at each visit and change from baseline Vital signs (blood pressure [BP], heart rate, and temperature) parameter results at each visit and change from baseline Clinical laboratory results and change from baseline Physical examinations changes from baseline ADAs Study drug

Section	Description of Changes	Rationale
		exposure/compliance • Concomitant medication usage
Secondary		

 To characterize the PK of BOS161721 and select the optimal dose of BOS161721 based on safety, PK, and PD effects in patients with mild to moderate SLE. 		Pharmacokinetic Endpoints 
 BOS161721 concentration by visit and time point Maximum observed concentration (C_{max}), T_{max}, area under the concentration-time curve (AUC), terminal elimination half-life ($t_{1/2}$), systematic clearance (C_L), volume of distribution (V_d) Pharmacodynamic Endpoints 
 Results and changes (or shifts) from baseline to each visit in phosphorylated signal transducer and activator of transcription 3 (pSTAT3), C3 and C4 levels, and leukocyte immunophenotype Results and changes (or shifts) from baseline in anti-double-stranded DNA (dsDNA), antinuclear antibodies (ANA), anti-Sjögren syndrome A and B (SSA, SSB), Smith (Sm), and antiphospholipid (APL) autoantibodies at each visit Results and changes (or shifts) from baseline in abrogation of IL-21 gene signature at each indicated visit
Exploratory		

 CCI [REDACTED] 	[REDACTED]	CCI [REDACTED]

Section	Description of Changes	Rationale	

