1.2.5 Potential Risks

Potential risks based on the mechanism of action of BOS161721 include infections, risks associated with the administration of any foreign protein or biologic agent, including injection site reaction, anaphylaxis, serious allergic reaction, and development of ADAs. ADAs could result in immune complex disease (with manifestations such as arthralgias, serum-sickness, and vasculitis), autoimmunity, or altered BOS161721 levels or activity. Further details can be found

in the current Investigator's Brochure (IB) for BOS161721, which contains comprehensive toxicology, preclinical and clinical information on BOS161721.

Two investigational drug products are considered to be in the same pharmacological class as BOS161721 based on interruption of signaling through the IL-21 signaling pathway. No potential risk generalizable across the class has been observed with these investigational products. Based on the clinical Phase 1 SAD study (BOS161721-01), AEs reported as related to the study drug, particularly infections (flu-like symptoms, etc), were expected for the compound, and there were no clinically relevant changes in laboratory and ECG results or vital signs.

The majority of IgG elimination occurs via intracellular catabolism, following fluid-phase or receptor-mediated endocytosis. This type of endocytosis and elimination is a form of target-mediated disposition where the interaction of the drug and its pharmacological target (eg, a target receptor) serves as a significant contributor to the kinetics of antibody distribution and elimination. Renal elimination, which is a primary pathway of clearance of small-molecule drugs, is relatively unimportant for IgG, as its large size prevents efficient filtration through the glomerulus. Secretion into the bile is an important pathway of elimination of IgA antibodies, but this route is not a significant contributor to the elimination of IgG antibodies. Thus, risk to renal and hepatic systems due to metabolism of BOS161721 is low.³³

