7.2.8 Immunogenicity

The serum samples to measure the presence of ADA will be collected as Visits 2, 3, 4, 6, 7, 10, and 13 (Week 0, 2, 4, 8, 12, 24, and 36, respectively). Blood samples (4 mL) to provide approximately 1.5 mL of plasma for anti BOS161721 antibody analysis will be collected into appropriately labeled tubes containing K₂EDTA. The presence or absence of ADA will be determined in the serum samples using validated bioanalytical methods. Blood samples for ADA analysis will be collected up to Day 90 from all patients. Subsequent ADA samples will be collected from all patients but only assayed if the patient had a positive ADA on Day 90.

After the first dose, if a patient tests positive in the validated confirmatory ADA assay, the sample from this patient will be further analyzed in the neutralizing antibody (nAb) assay.

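### Anti-drug antibody samples after Day 90 are drawn from everyone but assayed only in patients positive on Day 90, so antibodies first appearing later in treatment go undetected

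*Protocol*

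**What the plan says.** Section 6.2.8 (Immunogenicity) of the current protocol, V3.0, sets two rules. Up to Day 90: "Blood samples for ADA analysis will be collected up to Day 90 from all patients". After Day 90: "Subsequent ADA samples will be collected from all patients but only assayed if the patient had a positive ADA on Day 90". Testing in the neutralising assay follows a positive result only: "if a patient tests positive in the validated confirmatory ADA assay, the sample from this patient will be further analyzed in the neutralizing antibody (nAb)".

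The current dosing text, reproduced in Appendix 7 under Section 3.1, reads: "Patients may receive a total of 7 SC monthly doses of study drug on Days 0, 30, 60, 90, 120, 150, and 180".

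The Phase 1b primary objective (Section 2.1, reproduced in Appendix 7) is "To assess safety, tolerability, and immunogenicity of repeat doses of BOS161721", and ADAs are listed among its endpoints. ADAs are also listed among the Phase 2 safety endpoints.

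Section 6.2.8 refers to the Section 3.4 schedule for sampling days. That table is not in the part of the protocol at hand. The first protocol version gave the days in words, as "Week 0, 2, 4, 8, 12, 24, and 36, respectively", and the ADA rows of Tables 1 and 2 in Amendment 1 show Days 0, 15, 30, 60, 90, 180 and 270.

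**The concern.** The rule makes one sample, roughly halfway through treatment, decide whether any later sample is tested. A patient negative on that day goes on receiving drug for three more months, and the blood drawn afterwards is left unassayed. An objective about repeat doses is then answered for only the first part of the regimen.

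The sponsor's own risk text explains why this matters. Section 1.2.5 of the earlier version says "ADAs could result in immune complex disease", and adds altered drug levels or activity as a further possibility. The primary efficacy endpoint is at Day 210 (Section 8.2.3). For Day-90-negative patients, ADA status would be unknown over the 210 − 90 = 120 days before it, so a late loss of exposure or response in those patients could not be related to antibodies.

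A statistical analysis plan cannot repair this, because the rule determines which results exist.

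**Working it through.** The plan states no figure for ADA incidence or timing, so there is none to reproduce. The check compares the dosing days, the sampling days and the assay rule.

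**Inputs**
- Doses: Days 0, 30, 60, 90, 120, 150, 180 (seven; current text).
- ADA samples: Days 0, 15, 30, 60, 90, 180, 270 (superseded tables; taken as an assumption about the current schedule).
- Rule: samples after Day 90 are assayed only if Day 90 was positive (current Section 6.2.8).

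**Step 1: exposure not covered.** If the Day 90 sample is predose, it follows three doses (Days 0, 30, 60), and four doses (Days 90, 120, 150, 180) come after it. If it is postdose, the split is four and three. Section 6.2.8 does not say which applies to ADA.

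**Step 2: follow-up not covered.** Samples after Day 90 on the assumed schedule: two, Days 180 and 270. Share of follow-up with no ADA result in Day-90-negative patients: (270 − 90)/270 = 67%.

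**Step 3: other routes to a result.** The text at hand contains no clinical trigger, reflex test or retrospective assay for a Day-90-negative patient. The same rule appears in the schedule footnotes of both earlier versions, and the summary of changes records no alteration to it.

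**Step 4: direction and possible size.** Let p be the true cumulative incidence and f the share of converters first positive after Day 90. Then

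reported incidence = p × (1 − f).

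Since f cannot be negative, the bias is downward, or zero only if nobody first converts after Day 90. The documents give neither p nor f; the values below are assumptions.

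| True p | f = 10% | f = 25% | f = 50% |
|---|---|---|---|
| 5% | 4.5% | 3.8% | 2.5% |
| 10% | 9.0% | 7.5% | 5.0% |
| 20% | 18.0% | 15.0% | 10.0% |

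**Step 5: patients positive early and negative on Day 90.** Their Day 15, 30 or 60 positive has already been assayed, so they remain in any-time incidence. Whether the response persisted or recurred cannot be described.

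**The case against.** The best defence is one of relevance. The Phase 1b objective serves dose choice, and Section 8 places the interim analysis for that choice during the last ascending-dose cohort, so most late antibody data would arrive too late to inform it. In Phase 2, ADA is one safety endpoint among many. Day-90-positive patients are still followed, and anaphylaxis and serious allergic reactions are captured as events of special interest whatever the ADA status. This limits the consequences. It does not make incidence measured to Day 90 a description of a seven-dose regimen.

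A reader might also infer more than the documents support:

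- **That only about a third of cases would be found.** With a constant monthly conversion probability of 1% to 5%, 1 − (1 − h)³ gives 3.0% to 14.3% by month 3, against 1 − (1 − h)⁹ = 8.6% to 37.0% by month 9, or 34% to 39% detected. That ratio is largely built in by assuming a constant rate over three of nine months. If conversion comes mainly early, far more would be found. No document fixes the shape.
- **That patients positive early and negative on Day 90 drop out of the incidence, or that unassayed samples are recorded as negative.** The rule touches only samples after Day 90, and Section 6.2.8 says nothing about how unassayed samples are classified.
- **That the Day 270 sample is the one least masked by circulating drug.** Using the 44-day half-life in the earlier version's Section 1.2.3, with simple exponential decay and absorption ignored, summing 2^(−days since dose/44) over the doses given gives 0.62 single-dose units before the Day 30 dose and 0.62 at Day 270. The two are practically tied, and the Day 30 sample falls within the period tested in everyone.
- **That ADA relationships could not be examined at all.** They could be, in Day-90-positive patients and up to Day 90 in everyone.

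**Conclusion.** The point holds as a design defect in current text. Under the protocol as written, antibodies first appearing after Day 90 would not be detected, nor would their neutralising status, and later status is lost for patients who were positive earlier but negative on Day 90.

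The direction of the bias in cumulative incidence is certain: it cannot be upward. Its size is not derivable. The 9% to 5% reported for a true 10% rests entirely on the assumed 10% to 50% late share.

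The existence of the gap rests on current wording. The count of two later samples depends on the current schedule matching the superseded tables, and the split of doses depends on when the Day 90 sample is drawn. Because the endpoint belongs to a primary objective and the remedy is simple, the rule should be changed.

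**What to change.** Delete the Day 90 condition from Section 6.2.8 and from any schedule footnote that repeats it. Assay all ADA samples collected after Day 90 in every patient, with confirmatory and neutralising testing as already specified. Report treatment-emergent ADA incidence at any post-dose time through the last sample, and state whether the Day 90 sample is predose.

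The cost is laboratory work only: a few extra screening assays per patient, or about two if the current schedule keeps Days 180 and 270. With 30 + 156 = 186 planned patients, that is at most 2 × 186 = 372 assays, and fewer after dropouts and Day-90 positives, who are tested already. No visit or blood draw is added.

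A separate minor correction: Section 6.2.8 calls the ADA samples serum, yet also says "plasma for anti BOS161721 antibody analysis will be collected into appropriately labeled tubes containing" K2EDTA. The two should be reconciled to the matrix in which the assay is validated.

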6.3 Efficacy Assessments

All efficacy assessments will be performed at times defined in the Schedule of Assessments ([Section 3.4](#)).

6.3.1 SLEDAI-2K

The SLEDAI-2K is a validated instrument that measures disease activity in SLE patients at the time of the visit and in the previous 30 days. It is a global index and includes 24 clinical and laboratory variables that are weighted by the type of manifestation, but not by severity. The total score falls between 0 and 105, with higher scores representing increased disease activity. The SLEDAI-2K has been shown to be a valid and reliable disease activity measure in multiple patient groups. A SLEDAI -2K of 6 or more generally represents moderately to severely active disease.⁴⁴

6.3.2 BILAG 2004

The BILAG-2004 index is an organ-specific 97-question assessment based on the principle of the doctor's intent to treat. Only clinical features attributable to SLE disease activity are to be recorded and based on the patient's condition in the last 4 weeks compared with the previous 4 weeks. It will be scored as not present (0), improved (1), the same (2), worse (3), or new (4). Disease activity is graded separately for 9 body systems to 5 different grades (A to E) as follows: A ("Active") is very active disease, B ("Beware") is moderate activity, C ("Contentment") is mild stable disease, D ("Discount") is inactive now but previously active, and E ("Excluded") indicates the organ was never involved.⁴⁴ A shift from BILAG-2004 Grade A or B to a lower grade indicates a clinically relevant change in disease activity as the BILAG-2004 grades mirror the decision points for treatment interventions.

Only investigators that complete BILAG-2004 training will be allowed to perform the BILAG-2004 assessments. Preferably, the same investigator should evaluate the patient at each BILAG-2004 assessment from screening to study completion. The investigator must maintain documentation with descriptive details supporting the BILAG-2004 scoring (eg, chart, worksheet, clinic notes, and labs) at each visit.

See [APPENDIX 5](#) for detailed specifications.

6.3.3 PGA of Disease Activity

The PGA is used to assess investigator's general impression on the patient's overall status of SLE disease activity via visual analogue scale (100 mm) with 0 being "very good, asymptomatic and no limitation of normal activities" with 100 mm being "most severe possible disease ever seen in all SLE patients".

When scoring the PGA, the assessor should always look back at the score from the previous visit.

6.3.4 Composite Endpoints: SRI-4, SRI-5, SRI-6, and BICLA Response

6.3.4.1 SRI-4 Response

The SRI-4 is a composite index of SLE disease improvement that consists of scores derived from the SLEDAI-2K and the BILAG 2004 Index. Response based on the SRI-4 is defined by:

1) \geq 4-point reduction in SLEDAI-2K global score, 2) no new severe disease activity (BILAG A organ score) or more than 1 new moderate organ score (BILAG B), and 3) no deterioration from baseline in the PGA by \geq 0.3 points. The SRI-4 response in patients with moderate to severe SLE is associated with broad improvements in clinical and patient-reported outcomes.⁴⁵

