6.3.4.3 BICLA Response

The BICLA is a responder index developed to measure response to therapy, and it includes scores from the BILAG, SLEDAI-2K, and PGA. BICLA response is defined as 1) at least 1 gradation of improvement in baseline BILAG 2004 scores in all body systems with moderate disease activity at entry (eg, all B [moderate disease] scores falling to C [mild], or D [no activity]); 2) no new BILAG A or more than 1 new BILAG B scores; 3) no worsening of total SLEDAI-2K score from baseline; 4) \leq 10% deterioration in PGA score and 5) no treatment failure.⁴⁴ It is driven primarily by the BILAG, and has been used in Phase 2 and 3 mAb studies.⁴⁷

For the endpoints of BICLA response at Days 210, 240, and 270, patient scores will be completed and response determined.

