8.1 Sample Size

Sample size in the Phase 1b study is based on operational consideration.

The sample size in the Phase 2 study is based on the primary endpoint, SRI-4 Response at Day 210. Approximately 156 additional patients will be randomized in a 2:1 ratio to BOS161721 versus placebo to achieve 132 evaluable subjects in the FAS. This assumes 24 subjects will drop prior to having received treatment and an evaluable post-baseline efficacy measure. Enrollment and randomization will be monitored in a blinded fashion and increased if needed to ensure at least 132 subjects are randomized into the FAS.

A total of 132 subjects randomized provides more than 80% power to detect a treatment difference of 25% in SRI-4 response rates at Day 210, based on a targeted 2-sided significance level of 10% and using a 2-sided Pearson's chi-squared test. This assumes of a response rate of 65% for BOS161721 and 40% for placebo, where missing data at Day 210 is carried forward

from most recent non-missing result and subjects are treated as a non-responder if a prohibited medication defined as a medication failure occurs.

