8.2.3 Primary Efficacy Endpoint(s)

The proportion of patients who achieve a SRI-4 response at Day 210 will be assessed via Pearson's chi-squared analysis. The primary efficacy endpoint will be analyzed using the FAS and if needed repeated in the PP analysis set. Missing values will be addressed by employing a last observation carried forward (LOCF) analysis. Other imputation methods may be employed as a sensitivity analysis and will be described in the SAP. Additional analyses exploring impact of baseline factors such as baseline disease severity, race, and other characteristics may be performed.

Patients that received prohibited medications or unallowable CS usage as described in [Section 4.6](#) will be considered "medication failures" and will be treated as non-responders for the primary efficacy analysis. Patients that received an allowable CS burst but having missing data at Day 210 will considered a medication failure and will be treated as non-responders for the primary efficacy analysis. The determination of medication failures will be reviewed using blinded data and finalized prior to unblinding.

The superiority of BOS161721 relative to placebo will be evaluated. If the proportion of SRI-4 responders for the selected POC dose in BOS161721 arm is higher than that of the placebo arm, then BOS161721 will be considered superior to placebo if the 2-sided p-value is less than or

equal to 0.10. Secondary and exploratory endpoints for this POC study will be evaluated based on the same statistical hypothesis.

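### The SRI-4 PGA criterion is set at 0.3 points, but the PGA is collected on a 0-100 mm scale and the text shown gives no conversion

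*Protocol*

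**What the plan says.** Section 6.3.3 describes the PGA as the investigator's rating of "SLE disease activity via visual analogue scale (100 mm) with 0 being" the best state and 100 mm the worst. No other PGA scale appears in the text shown.

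Section 6.3.4.1 defines SRI-4 response by three conditions: a SLEDAI-2K reduction of at least 4 points, a limit on new BILAG A and B scores, and "no deterioration from baseline in the PGA by" at least 0.3 points. It does not say what a point is.

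Section 8.2.3 makes this the primary analysis: "The proportion of patients who achieve a SRI-4 response at Day 210 will be assessed via Pearson's chi-squared analysis".

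Two neighbouring definitions bear on the point. BICLA (6.3.4.3) uses the same PGA but tolerates up to "10% deterioration in PGA score and 5) no treatment failure". SRI-5 and SRI-6 (6.3.4.2) are introduced as being like SRI-4 with a different SLEDAI-2K requirement, and that section does not mention the PGA.

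**The concern.** A threshold has meaning only on a stated scale. Here the instrument is in millimetres from 0 to 100 and the cut is 0.3 of an undefined unit. Taken together as printed, the cut is finer than one millimetre of a 100 mm line. A patient whose SLEDAI-2K has fallen by 4 or more, with no disqualifying BILAG change, would then fail because the assessor's mark moved 1 mm the wrong way.

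What is at stake is who counts as a responder on the primary endpoint. Two programmers could classify the same patient differently, one applying 0.3 to the millimetre value and the other rescaling first. If that choice were made after unblinding it would be hard to defend.

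**Working it through.** **Unit check.**

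- Scale: 0 to 100 mm (6.3.3). Cut: 0.3 points (6.3.4.1).
- If one point is one millimetre, the only unit given: 0.3 / 100 = 0.3% of the range. The smallest whole-millimetre worsening, 1 mm, exceeds 0.3 and fails.
- Assumption: the cut was meant for a 0-3 scale. Then 0.3 / 3 × 100 = 10 mm, and the literal cut is 10 / 0.3 = 33 times stricter.
- Assumption: the cut was meant for a 0-10 scale. Then 0.3 / 10 × 100 = 3 mm, and the literal cut is 3 / 0.3 = 10 times stricter.

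**The plan's own power.** Section 8.1 states "A total of 132 subjects randomized provides more than 80% power to detect a treatment difference of 25" percentage points, with 65% against 40%, two-sided alpha 0.10, a Pearson chi-squared test and 2:1 allocation, which makes 88:44 of the 132.

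- Formula: power = Φ[(d − 1.645 × s0) / s1], where s0 is the standard error from the pooled rate and s1 the standard error from the separate rates.
- Pooled rate: (88 × 0.65 + 44 × 0.40) / 132 = 0.567.
- s0 = √[0.567 × 0.433 × (1/88 + 1/44)] = 0.0915.
- s1 = √[0.65 × 0.35 / 88 + 0.40 × 0.60 / 44] = 0.0897.
- Power = Φ[(0.25 − 1.645 × 0.0915) / 0.0897] = 86.6%. Exact enumeration of the test gives 86.3%. The claim of more than 80% is reproduced.

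**Illustration with equal loss.** Assumption: the strict rule removes the same share f of responders in both arms, so both planned rates are multiplied by 1 − f. Same formula:

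| f | Active | Placebo | Difference (points) | Power |
|---|---|---|---|---|
| 0 | 65.0% | 40.0% | 25.0 | 86.6% |
| 5% | 61.75% | 38.0% | 23.75 | 83% |
| 10% | 58.5% | 36.0% | 22.5 | 79% |
| 20% | 52.0% | 32.0% | 20.0 | 71% |

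**Illustration with unequal loss.** The shares are again assumed.

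- Active loses 5%, placebo 15%: 0.65 × 0.95 = 61.75% and 0.40 × 0.85 = 34.0%. The difference widens to 27.75 points and power is about 92%.
- Active loses 15%, placebo 5%: 55.25% and 38.0%. The difference narrows to 17.25 points and power is about 59%.

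The protocol gives no distribution of PGA change, so it does not say which of these cases, if any, would apply.

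**The case against.** **Points need not be millimetres.** The protocol nowhere equates them, and another scale may have been intended. This stands. The firm finding is the mismatch; the 1 mm consequence follows only when the cut is read on the one scale given.

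**A conversion may exist elsewhere.** Only the last of three parts of the protocol is at hand, the current objectives and endpoints section is not in it, and Section 8 leaves transformations to the SAP. A conversion there is possible. It would still leave 6.3.4.1 stating a threshold in a unit that the instrument in 6.3.3 does not have. The superseded versions reproduced after the appendices carry the same pair of statements, so the mismatch has persisted through amendment.

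**A reader might infer that the cut should be 10 mm.** The documents do not support this. No 0-3 scale appears in the text shown, and a 0-10 scale would give 3 mm.

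**A reader might take BICLA's 10% as confirmation of 10 mm.** It may instead mean 10% of the patient's own baseline score, for example 4 mm from a baseline of 40 mm. It shows that the two composites need reconciling, but not what the SRI-4 cut should be.

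**A reader might infer that the trial is underpowered or that the treatment difference must shrink.** That needs an equal or unfavourable loss across arms, which the protocol cannot show; the unequal case above can widen the difference. Nor does Section 8.1 name a source or a PGA scale for the 65% and 40%, so it cannot be said that those rates rest on a different endpoint.

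**Conclusion.** The concern holds as a mismatch between threshold and instrument in a component of the primary endpoint. On the only scale in the text shown, the cut is 0.3% of the range and a 1 mm worsening fails the patient. Against the two candidate scales, both assumed, the literal rule is 10 to 33 times stricter.

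The sample-size arithmetic is sound. The power figures of 83%, 79% and 71% rest on an assumed equal proportional loss and show only that the issue could matter. They do not estimate a loss in this trial, and neither the size nor the direction of the effect on the treatment difference can be derived from the document.

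That SRI-5 and SRI-6 carry the same PGA component is likely from their description, but it is not stated.

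**What to change.** Have the sponsor confirm the scale for which 0.3 was intended. Then, before unblinding, rewrite the third component in 6.3.4.1 in millimetres on the collected scale, or keep 0.3 points and state the conversion from the 100 mm line. Use the same wording in 6.3.4.2 if SRI-5 and SRI-6 share the component. In 6.3.4.3, say whether the 10% is of the scale or of the baseline score.

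The cost is one sentence for the primary criterion, the matching clarifications, and a line in the programming specification. The PGA is already scheduled in millimetres, so no new data are needed.
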